## 5.2 Secondary Efficacy Endpoints

- Diagnosis of venous thromboembolism (pulmonary embolism and/or deep venous thromboembolism)
- Nonreceipt or delay of neuraxial anesthesia due to unfractionated heparin defined as inability to receive neuraxial anesthesia due to an elevated aPTT value or because the subject received heparin
- Receipt of general anesthesia due to unfractionated heparin
- Delay in timing of delivery due to unfractionated heparin defined as presence of an indication to proceed with delivery via cesarean delivery or induction of labor but this does not immediately occur due to an elevated aPTT value or because the subject received heparin
- Mode of delivery
- Estimated blood loss at time of delivery
- Receipt of blood transfusion
- CBC for hemoglobin and platelet count (to be assessed weekly while receiving unfractionated heparin)
- Anti-Xa levels (to be assessed with aPTTs while receiving unfractionated heparin)
- Goal anti-Xa level achieved (0.2-0.5 IU/mL)
- Number of times adjustment in dose made
- Development of side effects from heparin administration (e.g bruising, epistaxis)
- Neonatal outcomes
  - Gestational age at delivery
  - Birthweight
  - 1 minute and 5 minute APGAR scores
  - Cord blood gas values: umbilical artery pH, umbilical artery CO2, umbilical artery base excess
  - NICU admission
  - Neonatal death

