## **10.4 Visit 4: Day 6**

1. Record any Adverse Experiences or side effects
2. Record times when patient received unfractionated heparin or had noncompliance to medication
3. Collect CBC, aPTT, and anti-Xa 6 hours after tenth dose of heparin (~15:00 PM on day 6)
4. Follow up aPTT
  - a. If  $<$  36.2 seconds, continue current dose of heparin
  - b. If  $\geq$  36.2 seconds, adjust heparin dose and repeat aPTT and anti-Xa per protocol (APPENDIX 1)

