### **11.4 Analysis of Secondary Endpoints**

Comparison of maternal demographics, baseline characteristics, additional maternal outcomes, and neonatal outcomes between the two groups will be analyzed using Student's t-test for parametric data, Wilcoxon signed-rank test for nonparametric data, and Chi-squared or Fisher's exact test for comparison of proportions. Descriptive statistics will be performed to summarize which dose resulted in a normal aPTT value and anti-Xa within goal range. Multivariate logistic regression analysis will be performed to determine which factors were associated with an elevated aPTT value. Statistical significance will be set at a p-value of  $< 0.05$  or 95% confidence interval not overlapping.

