### **11.5 Sample Size and Randomization**

Based on an informal/pilot review of antepartum admissions at our institution receiving gestational age-based dosing of unfractionated heparin, 40% of patients and an elevated aPTT

value. Assuming 40% of patients receiving gestational age-based dosing and 3% receiving standard dosing had elevated serum aPTT values, a sample size of 18 women in each dosing group would have 80% power (alpha = 0.05) to demonstrate a significant difference in our primary outcome of evaluating the proportion of women with elevated aPTT values after heparin administration. We increased the sample size by 25% to account for post-randomization drop-out or lab sampling errors. We plan to recruit 46 patients.

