Title of Study: Heparin Prophylaxis Dosing for Antepartum Hospitalizations (HEPDOSE)

NCT Number: NCT04635839

Document Date: June 27, 2022

Document: Statistical Analysis Plan

Traditional univariate analysis was performed for our primary and secondary outcomes with Chi-square or Fisher exact test for categorical variable and t-test or Wilcoxon rank-sum test for continuous variables. A logistic regression analysis was performed to further assess the association of elevated aPTT with gestational age-based dosing of unfractionated heparin relative to standard dosing. We also performed a multivariate logistic regression to adjust for confounders. Confounders included in the model were a priori covariates that potentially could affect the response to unfractionated heparin along with baseline characteristics from our univariate analyses comparing study arm groups that had a p value < 0.2. Via a stepwise regression, none of the variable demonstrated a significant effect on our primary outcome. However, for our final model we elected to adjust for creatinine and obesity based on clinical relevance and a priori knowledge of these factors being potential confounders that may not have been detected in our study cohort due to the small sample size.

Statistical significance was defined as a p-value of < 0.05 or non-overlapping 95% confidence intervals (CI). All analyses were conducted using Statistical Analysis Software (SAS), version 9.4 (Copyright 2013, SAS Institute, Inc. Cary, NC).

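### Anti-Xa and CBC are measured serially, and triggered repeat anti-Xa draws would fall mainly in arm 2, yet the plan names only simple group-comparison tests and no draw that decides the endpoint

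*SAP*

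**What the plan says.** Protocol 5.2 lists two anti-Xa endpoints: "Anti-Xa levels (to be assessed with aPTTs while receiving unfractionated heparin") and "Goal anti-Xa level achieved (0.2-0.5 IU/mL"). Hemoglobin and platelets are a further secondary endpoint, measured weekly. None of these has a time point or a per-woman summary.

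Protocol 10.2 to 10.5 and Appendix 2 set the schedule. Post-dose anti-Xa is drawn once on Day 2 (6 hours after dose 2), twice on Day 3 (2-hour peak and 6-hour value), once on Day 6, then weekly until delivery or discharge. CBC is drawn on Day 1, Day 6 and weekly. At each visit a high aPTT leads to a changed dose and a further sample; 10.4, for instance, says to "adjust heparin dose and repeat aPTT and anti-Xa per protocol". CBC is not among the repeated tests.

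On analysis, Protocol 11.4 reads "Comparison of maternal demographics, baseline characteristics, additional maternal outcomes, and neonatal outcomes between the two groups will be analyzed using" Student's t-test, a Wilcoxon test, and chi-squared or Fisher's exact test. It adds a descriptive summary of which dose gave an in-range anti-Xa. The SAP names chi-square or Fisher for categorical outcomes and "t-test or Wilcoxon rank-sum test for continuous variables". No repeated-measures method appears in either document.

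**The concern.** The named tests assume one independent value per woman, but the data will not arrive that way. A woman who leaves on Day 3 has three scheduled post-dose anti-Xa values; one who stays to Day 27 has seven. The number of draws also depends on the arm, because repeats are triggered by the primary outcome, and those repeats are taken after the assigned dose has been changed.

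The anti-Xa result matters. Protocol section 2 hypothesises no significant difference between arms in reaching the goal range, and objective 3.2(b) relies on anti-Xa in range to judge dosing. VTE is also a secondary endpoint, but at the stated risk below 2% fewer than 46 x 0.02 = 0.92 events are expected, so anti-Xa carries most of the information on adequacy of prophylaxis. With the deciding draw left open, it could be chosen after the results are seen, and that choice can move the comparison.

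**Working it through.** **Inputs from the documents.** Protocol 11.5 gives the planning rates: "Assuming 40% of patients receiving gestational age-based dosing and 3% receiving standard dosing had elevated serum aPTT values". Its stated size is 18 per arm, for 80% power at alpha 0.05. On attrition it says: "We increased the sample size by 25% to account for post-randomization drop-out or lab sampling errors"; 46 recruited, 23 per arm. Draw schedule as above.

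**Assumptions (not in the documents).** Within-woman correlation rho 0.3 to 0.7; a 20% chance per draw of being in goal range, equal in both arms and constant over draws; one or two triggered repeats per woman with a high aPTT. The content of Appendix 1, which governs repeats, is not shown in the text available to us.

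**1. The plan's own figure.** Two-sided pooled test at 18 per arm, mean proportion 0.215: z = [0.37 x sqrt(18) - 1.96 x sqrt(2 x 0.215 x 0.785)] / sqrt(0.40 x 0.60 + 0.03 x 0.97) = (1.570 - 1.139) / 0.519 = 0.83, so power is 79.7%. The stated 80% reproduces. 18 x 1.25 = 22.5, rounded to 23. No figure is given for anti-Xa or CBC.

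**2. Who has triggered repeats.** Arm 2: 23 x 0.40 = 9.2 women. Arm 1: 23 x 0.03 = 0.7.

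**3. If every draw were entered as independent.** Design effect = 1 + (m - 1) x rho; the naive standard error is 1/sqrt(design effect) of the correct one; type I error = 2 x [1 - Phi(1.96 / sqrt(design effect))].

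| Draws m | rho | Design effect | SE ratio | Type I error |
|---|---|---|---|---|
| 2 | 0.3 / 0.7 | 1.3 / 1.7 | 0.88 / 0.77 | 8.6% / 13.3% |
| 4 | 0.3 / 0.7 | 1.9 / 3.1 | 0.73 / 0.57 | 15.5% / 26.6% |
| 6 | 0.3 / 0.7 | 2.5 / 4.5 | 0.63 / 0.47 | 21.5% / 35.6% |

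A simulation with 18 women per arm, no true difference and 40% v 3% given one extra draw agrees: at m = 4 the pooled t-test rejects in 15.5% (rho 0.3) to 26.7% (rho 0.7) of 1,500 runs. A t-test on one mean per woman rejects in about 4-6% across the settings tried.

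**4. If the goal means ever in range.** With four scheduled draws, k repeats and independent draws, the ever-in-range rate is 1 - 0.8^4 = 59.0% without repeats and 1 - 0.8^(4+k) with them. For k = 2 the latter is 73.8%, so:
- arm 2: 59.0 + 0.40 x 14.7 = 64.9%
- arm 1: 59.0 + 0.03 x 14.7 = 59.5%
- difference: 0.37 x 14.7 = 5.5 points

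For k = 1 it is 0.37 x 8.2 = 3.0 points. Independence is the extreme case. With a latent-normal within-woman correlation of 0.3 to 0.7, the difference is 3.8 to 2.0 points for two repeats and 2.1 to 1.1 points for one. In an arm of 23, 3.8 points is 0.9 of a woman.

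**The case against.** The strongest reply is that the documents describe no faulty analysis. A reader might infer that draws will be pooled and the standard errors will therefore be too small, but no text says so. Protocol 11.1 defines the analysis set in patients, 11.3 scores the primary endpoint by whether an elevation occurred, and Appendix 2 lists peak and trough on separate rows, which makes indiscriminate pooling less likely. A two-sample test on one value per woman is valid. This stands: the inflation in step 3 is conditional.

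A reader might also infer that arm 2 is favoured on the goal endpoint. That needs an ever-in-range rule, which is not written. It also needs repeats to behave like fresh draws, whereas they follow a changed or held dose in women with a high aPTT, who may already be in or above range or may fall below it. The direction is therefore not established. The endpoint is binary, so chi-square or Fisher applies to it and not the t-test clause. CBC is outside the trigger, so only the serial-measurement point reaches it.

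Finally, section 2 calls the anti-Xa comparison exploratory, VTE is also measured, and the primary endpoint is untouched. All true, and they limit the weight of the point. They do not supply the missing definition, nor do they remove the arm-dependent number of draws.

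**Conclusion.** The point holds as a gap in the plan. Serial anti-Xa and CBC are assigned to simple group tests with no deciding draw, and triggered repeat anti-Xa samples would be very unequal by arm (about 9 v fewer than 1 of 23 at the planning rates). The consequences depend on how the gap is filled. Pooling four draws per woman would give a type I error of about 16-27% for rho 0.3-0.7, while one value per woman keeps it near 5%. Ever-in-range scoring would be worth about 1-4 points to arm 2 with correlated draws, and up to 5.5 if they were independent, assuming a constant 20% chance per draw and one or two repeats. What dose changes do to that difference could go either way.

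The documents do not support saying that the standard errors are too narrow, that the goal comparison is biased towards arm 2, or that anti-Xa is the trial's only measure of prophylaxis. The change is worth making because it does more than record a definition: it removes the unequal number of attempts and uses the serial and baseline data properly.

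**What to change.** In Protocol 11.4 and the SAP:

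- Compare anti-Xa level and goal achievement at one scheduled draw per woman, 6 hours after dose 2, which precedes any aPTT-guided change. Report the Day 3 peak separately.
- As support, fit a linear mixed model to the scheduled anti-Xa draws with a random effect for woman. Exclude triggered repeats, and state that later scheduled values may follow a dose change.
- Compare Day 6 hemoglobin and platelets by ANCOVA on the Day 1 value.

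The data are already collected under the schedule and the methods are standard in SAS, so the cost is wording and some re-analysis. There are three downsides. Later draws become supportive, although they bear on objective 3.2(b). Women who leave before Day 6 have no follow-up CBC and drop out of the ANCOVA. And because the SAP is written in the past tense and reports findings, a draw chosen after the data were seen should be labelled post hoc.

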#### **3.2 Secondary Objectives**

The secondary objective of this study is to evaluate pharmacokinetics and pharmacodynamics of unfractionated heparin in pregnancy.

- a) Determine the frequency of adjusted unfractionated heparin dosing based on elevated aPTT values and assess maternal characteristics associated with elevated aPTT values.
- b) Determine the appropriate dosing of unfractionated heparin for pharmacologic thromboprophylaxis of hospitalized antepartum patients (anti-Xa levels within prophylactic goal range, normal aPTT).

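### Outside its a priori list, the SAP admits characteristics to the multivariate aPTT model by chance imbalance between randomised arms, so its finding that no variable mattered covers only the variables entered

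*SAP*

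**What the plan says.** Protocol section 3.2(a) sets out to "assess maternal characteristics associated with elevated aPTT values". Section 11.4 gives the job to one model: "Multivariate logistic regression analysis will be performed to determine which factors were associated with an elevated aPTT value". The same section also plans tests between the two arms on baseline characteristics.

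The SAP presents its multivariate model as adjustment for confounders. Variables reach it by two routes:

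- **A priori:** "Confounders included in the model were a priori covariates that potentially could affect the response to unfractionated heparin". No list is given; only creatinine and obesity are identifiable, from the sentence on the final model.
- **Screened:** "baseline characteristics from our univariate analyses comparing study arm groups that had a p value < 0.2".

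The SAP then reports a selection step: "Via a stepwise regression, none of the variable demonstrated a significant effect on our primary outcome". It closes with the model it kept: "for our final model we elected to adjust for creatinine and obesity based on clinical relevance". It describes no other analysis of which characteristics relate to aPTT, although protocol section 11 says the SAP will describe all analyses.

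**The concern.** The screening test asks whether a baseline characteristic has the same distribution in the two arms. Allocation is randomised 1:1 (protocol section 8.1), so the null hypothesis is true by design and any difference is chance. The inputs are the arm and the baseline value. A characteristic with no effect on aPTT and one with a very strong effect have the same chance of passing.

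At stake is the answer to objective 3.2(a). A real predictor that is balanced between arms, which is the usual case under randomisation, never becomes a candidate unless it is on the a priori list. The stepwise step does use aPTT, but it cannot recover a variable that was not entered. The SAP's sentence that nothing had a significant effect can then be taken as a negative result for characteristics that were never examined. Irrelevant characteristics that happen to differ between arms are admitted as confounders.

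**Working it through.** **Inputs from the documents.** Screening threshold 0.2 (SAP); 1:1 randomisation (protocol 8.1); 40% v 3% with an elevated aPTT, 18 evaluable per arm, 80% power, alpha 0.05, 25% inflation and 46 recruited (protocol 11.5).

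**Assumptions.** Two-sided alpha; odds ratios per SD of the characteristic; the prevalence of binary characteristics; the number of characteristics screened.

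**1. The plan's own figure.** The documents give no figure for how often a characteristic is left out. The sample size supplies the setting and is reproduced first. With a mean rate of (0.40 + 0.03)/2 = 0.215 and a difference of 0.37:

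n = [1.96 × √(2 × 0.215 × 0.785) + 0.842 × √(0.40 × 0.60 + 0.03 × 0.97)]² / 0.37² ≈ 18.1 per arm

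This rounds up to 19; power at 18 per arm is 79.7%. Inflation gives 18 × 1.25 = 22.5, hence 23 per arm and 46 in all. The plan's figures hold.

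**2. Chance of being left out.** Under randomisation the p-value for a baseline difference is approximately uniform, so P(p ≥ 0.2) = 1 − 0.2 = 0.80. Simulation (continuous) and exact enumeration (binary, prevalence 10 to 50%) at 18 and 23 per arm give:

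| Test between arms | Left out |
|---|---|
| t-test | 79.7–80.1% |
| Wilcoxon rank-sum | 80.1–81.6% |
| Chi-square, uncorrected | 75.7–81.4% |
| Fisher exact | 86.7–95.3% |

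The continuous rows cover odds ratios per SD of 1, 3 and 10, and the rate does not move with the strength of the effect. For contrast only, a p<0.2 screen against aPTT itself would leave out a characteristic with an odds ratio of 3 per SD 27% of the time (18 per arm) or 19% (23 per arm).

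**3. Illustrative loss of power.** 4,000 simulated trials per setting; normal covariate; marginal rates 3% and 40%; likelihood-ratio test of the covariate adjusted for arm, at 0.05. The screened figure is the chance of passing the t-test screen and then reaching significance.

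| Odds ratio per SD | 23/arm: direct | 23/arm: screened | 18/arm: direct | 18/arm: screened |
|---|---|---|---|---|
| 2 | 38.8% | 8.0% | 32.0% | 6.3% |
| 3 | 67.1% | 13.1% | 58.0% | 11.4% |
| 4 | 82.7% | 16.3% | 71.8% | 13.7% |

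The screened figures are close to one fifth of the direct ones (for example 0.2 × 67.1% = 13.4%), as expected when the screen is unrelated to the outcome. The direct test was slightly oversized (6.2 to 6.6% at an odds ratio of 1).

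**4. Admission by luck.** If 10 independent characteristics were screened, at least one would pass with probability 1 − 0.8¹⁰ = 89%. With 10 binary characteristics under Fisher the range is 1 − 0.953¹⁰ = 38% to 1 − 0.867¹⁰ = 76%.

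**5. A constraint on any remedy.** At the assumed 3%, the standard arm has no events with probability 0.97²³ = 50% (23 per arm) or 0.97¹⁸ = 58% (18 per arm). Ordinary maximum likelihood then gives no finite estimate for arm. Expected events in total are 0.43 × 18 = 7.7 to 0.43 × 23 = 9.9.

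**The case against.** The strongest reply is about purpose. The SAP calls this a confounder-adjusted model of the dose effect, and a predictor balanced between arms causes little chance confounding of that effect. This stands as far as the dose effect goes. It does not answer the protocol, which gives the multivariate model the task of finding factors associated with aPTT and for which the SAP offers no other analysis.

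A reader might infer that the screen distorted the reported dose effect. The documents do not support that. The primary analysis is an unadjusted comparison of arms (protocol 11.3), and the final model adjusts for creatinine and obesity on stated clinical and a priori grounds. No screened variable remains in it.

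A reader might also infer that any true driver of aPTT was missed 80% of the time. That is too broad. The a priori route is meant for suspected drivers, and the examples in the protocol's hypothesis (section 2: eGFR and BMI) correspond to creatinine and obesity. Because the list is not spelled out, nobody can say whether age, gestational age or parity faced the screen, so the exclusion rate cannot be attached to a named characteristic.

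Two further points stand in part. The SAP does caution that the small sample may have hidden effects, so it does not claim absence of effect outright; but that caution concerns sample size, not variables that were never entered. And the variables in protocol 11.2 overlap (height, weight and BMI; gravida and parity), so 10 independent characteristics is only an illustration.

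**Conclusion.** The entry rule is wrong for the question the protocol asks. For characteristics outside the a priori list, entry is decided by chance: about 80% are left out if continuous, 76 to 81% if binary under uncorrected Chi-square, and 87 to 95% under Fisher, regardless of their relation to aPTT. The SAP's statement that "none of the variable demonstrated a significant effect on our primary outcome" is evidence only about the variables entered.

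The reach is limited. The dose comparison and the final adjusted model do not depend on the screen, and protocol section 2 treats these associations as exploratory. The exclusion rates rest on randomisation; since the analysis set is defined after randomisation (protocol 11.1), they are approximate if exclusions differ by arm. The power losses rest on assumed odds ratios of 2 to 4 per SD and are illustrations, not estimates for this trial. How many characteristics faced the screen is unknown.

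**What to change.** - **SAP, entry rule:** delete the p<0.2 between-arm criterion. Keep the covariates for the adjusted dose effect to those chosen a priori, creatinine and obesity.
- **SAP, objective 3.2(a):** for each baseline characteristic already collected (protocol 11.2, and creatinine at Visit 1), fit a logistic model with arm plus that characteristic. Report each odds ratio with its 95% confidence interval, labelled exploratory and unadjusted for multiplicity. Use a penalised (Firth) or exact fit because the standard arm may well have no events.
- **SAP, negative statement:** limit it to the variables actually entered and name them.
- **Protocol 11.4:** summarise baseline characteristics by arm descriptively, without tests between arms.

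The SAP is written in the past tense, so this means re-analysis and rewording, and the added models should be described as post hoc. No new patients, samples or procedures are needed, and the primary comparison is unchanged. The cost is several exploratory estimates with wide intervals and some risk of a false positive: with six independent null characteristics, 1 − 0.95⁶ = 26% at a true 5% level, or 32 to 34% at the 6.2 to 6.6% size seen in simulation for the ordinary likelihood-ratio test.

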STATISTICS Primary Analysis Plan	
Analysis of the primary endpoint of whether or not there was an elevation in aPTT in each dosing group will be performed with a Chi-squared test. Multivariate logistic regression analysis will be performed to determine which factors were associated with an elevated aPTT value. Comparison of maternal demographics, baseline characteristics, additional maternal outcomes, and neonatal outcomes between the two groups will be analyzed using Student's t-test for parametric data, Wilcoxon signed-rank test for nonparametric data, and Chi-squared or Fisher's exact test for comparison of proportions. Descriptive statistics will be performed to summarize which dose resulted in a normal aPTT value and anti-Xa within goal range. Statistical significance will be set at a p-value of < 0.05 or 95% confidence interval not overlapping.

Rationale for Number of Subjects	
Assuming 40% of patients receiving gestational age-based dosing and 3% receiving standard dosing have an elevated aPTT value, a sample size of 36 women (18 in each arm) would have 80% power to demonstrate a significant difference between the proportion of women with elevated aPTT values after administration. We plan to recruit 46 (23 in each arm) to account for post-randomization drop out and lab sampling errors.

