## 2 STUDY RATIONALE

VTE is one of the leading causes of maternal morbidity and mortality. In efforts to decrease rates of VTE, there is an increased emphasis on administering pharmacologic thromboprophylaxis for antepartum patients with prolonged hospitalizations. Due to physiological changes of pregnancy that may alter the metabolism of unfractionated heparin, it is suspected that dosing of pharmacologic thromboprophylaxis may need to be altered. ACOG's current recommendation is to consider gestational age-based dosing of unfractionated heparin for hospitalized pregnant patients rather than standard dosing. However, there are no prior studies assessing the potential effects of higher dosing. Potential effects of higher dosing include limited receipt of neuraxial anesthesia, increased administration of general anesthesia, delayed time to delivery, and increased bleeding risk. We propose this study to provide a direct comparison of gestational age-based unfractionated heparin dosing to standard dosing of unfractionated heparin for pharmacologic thromboprophylaxis of hospitalized antepartum patients.

For our primary objective, we hypothesize that compared to standard dosing, gestational age-based dosing for VTE prophylaxis is associated with higher rates of elevated aPTT values, a surrogate marker of ineligibility for neuraxial anesthesia. For our additional exploratory objectives, we hypothesize that there will be no significant difference in achieving goal anti-Xa levels (0.2-0.5 IU/mL) between standard dosing and gestational age-based dosing and that particular characteristics (e.g., increased eGFR and higher BMI) are associated with elevated aPTT values with unfractionated heparin administration.

ACOG Practice Bulletin No.123. Thromboembolism in Pregnancy. *Obstet Gynecol* 2011;118:718-729.

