### **10.1 Visit 1: Day 1**

1. Review the study with the subject (subject's legal representative) and obtain written informed consent and HIPAA authorization and assent, if appropriate.
2. Assign the subject a unique screening number.
3. Record demographics data.
4. Record medical and surgical history
5. Record concomitant medications.
6. Collect blood for clinical laboratory tests (CBC, aPTT, anti-Xa, serum creatinine).
7. Randomize subject
8. Order unfractionated heparin dosing that subject is randomized to (first dose ordered for 21:00 PM the day patient is randomized)

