## **10.2 Visit 2: Day 2**

1. Record any Adverse Experiences
2. Record times when patient received unfractionated heparin or noncompliance to medication
3. Collect blood for aPTT and anti-Xa 6 hours after second dose of heparin (~15:00 PM on day 2)
4. Follow-up aPTT
  - a. If  $<$  36.2 seconds, continue current dose of heparin
  - b. If  $\geq$  36.2 seconds, adjust heparin dose and repeat aPTT, anti-Xa, and serum creatinine per protocol (APPENDIX 1)

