## **11 STATISTICAL METHODS AND CONSIDERATIONS**

Prior to the analysis of the final study data, a detailed Statistical Analysis Plan (SAP) will be written describing all analyses that will be performed. The SAP will contain any modifications to the analysis plan described below.

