### **11.2 Demographic and Baseline Characteristics**

The following demographic variables will be collected at screening: age, height and weight, body mass index, race, ethnicity. The following baseline characteristics will be collected at screening: gestational age at randomization, gravida, parity, maternal comorbidities.

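### The creatinine- and obesity-adjusted arm odds ratio was settled after a null stepwise search yet is described as a priori, and the logistic model has no stated provision for a zero cell, about an even chance at the plan's own 40% v 3%

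*SAP*

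**What the plan says.** Protocol section 11 sets the timing: "Prior to the analysis of the final study data, a detailed Statistical Analysis Plan (SAP) will be written". It allows the SAP to modify the plan. The primary test in section 11.3 is a Chi-squared test.

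The protocol's only regression appears in the Synopsis and again in section 11.4: "Multivariate logistic regression analysis will be performed to determine which factors were associated with an elevated aPTT value". That is a search for correlates. No covariates are listed and no adjusted arm effect is planned. Section 2 hypothesises that "particular characteristics (e.g., increased eGFR and higher BMI) are associated with elevated aPTT values", among the exploratory objectives.

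The SAP, dated June 27, 2022, is written in the past tense. It describes univariate tests (Chi-square or Fisher for categorical outcomes), a logistic regression for the arm effect, and a multivariate logistic regression adjusting for confounders. The candidates were unnamed a priori covariates plus "baseline characteristics from our univariate analyses comparing study arm groups that had a p value < 0.2". After the stepwise step, "none of the variable demonstrated a significant effect on our primary outcome. However, for our final model we elected to adjust" for creatinine and obesity. The SAP names SAS 9.4, but no exact or penalised estimator and no rule for an arm without events.

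**The concern.** There are two separate matters.

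First, the order of events. The SAP describes a search, a null result and then a choice of covariates, and it justifies that choice by a priori knowledge. A reader could take the adjusted odds ratio as pre-specified when no document fixed its covariates beforehand. The between-arm screen is also a poor way to choose adjusters in a randomised trial: a p-value comparing baseline characteristics between randomised arms measures chance imbalance, not prognostic value.

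Second, the estimator. If ordinary maximum likelihood is used and one arm has no events, the arm odds ratio is infinite and its Wald interval is uninformative. The plan expects 3% events in an arm of 18 to 23 women, so this was a foreseeable outcome of the design.

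**Working it through.** **Inputs.** Protocol section 11.5: 40% v 3%, 18 per arm, 80% power, alpha 0.05 (two-sided assumed), inflated by 25%. Section 4.1: 23 per arm. Section 11.1: the analysis set needs two doses and at least one aPTT, so 18 to 23 per arm is a plausible range. The 3% has no stated source, so 5% and 10% are shown as assumptions.

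**The plan's own figure.** n = [1.960·√(2p̄q̄) + 0.842·√(p₁q₁ + p₂q₂)]² / (p₁ − p₂)², with p̄ = 0.215:
- 1.960·√0.3376 = 1.139 and 0.842·√0.2691 = 0.437
- (1.139 + 0.437)² / 0.37² = 18.1, or 19 per arm rounded up, against the stated 18
- power at 18 per arm is 79.7%, and 18 × 1.25 = 22.5, rounded up to 23, giving 46

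The design reproduces.

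**Chance that the unadjusted odds ratio is not finite.** This is the exact probability that an arm has 0 or n events. It is essentially (1 − p)ⁿ for the standard arm, because 0.6¹⁸ is about 0.0001.

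| Standard-arm rate | 18 per arm | 23 per arm |
|---|---|---|
| 3% (plan) | 0.97¹⁸ = 57.8% | 0.97²³ = 49.6% |
| 5% (assumed) | 39.7% | 30.7% |
| 10% (assumed) | 15.0% | 8.9% |

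For the model with arm, obesity and creatinine, a simulation at 40% v 3% (3,000 trials per setting, obesity assumed 20–60%, no covariate effects) found at least one non-finite coefficient in about 58–66% of trials at 18 per arm and 49–57% at 23. The Monte Carlo standard error is at most 0.9 points.

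**Events per term.** Expected events are 18 × 0.43 = 7.74 or 23 × 0.43 = 9.89. Over three terms that is 2.6 or 3.3 each.

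**The remedy, by exact enumeration of the unadjusted model.** Across the six settings in the table, the Firth 95% profile-likelihood interval covers in 95.4–96.8%. Rejection probabilities at 40% v 3%:

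| Test | 18 per arm | 23 per arm |
|---|---|---|
| Firth | 85.4% | 93.7% |
| Uncorrected Chi-squared | 85.4% | 93.7% |
| Fisher | 74.9% | 88.2% |

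Every table that Fisher rejects, Firth also rejects. Firth alone is therefore significant in 10.5 or 5.5 percentage points of trials.

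**Illustration only, 9/23 v 0/23.** Maximum likelihood does not converge (log odds ratio standard error about 761). Firth gives 30.8, profile interval 3.4 to about 4,080. The exact conditional interval runs from 2.6 to infinity. Fisher p = 0.0015.

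**Screen.** Section 11.2 names ten baseline variables: age, height, weight, BMI, race, ethnicity, and "gestational age at randomization, gravida, parity, maternal comorbidities". Under randomisation about 10 × 0.2 = 2.0 pass p < 0.2 by chance. If they were independent, at least one would pass with probability 1 − 0.8¹⁰ = 89%; height, weight and BMI are not independent, so that figure is rough.

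**The case against.** The SAP hides nothing about the sequence: it says that the search found nothing and that the authors then elected the covariates. Renal function and body size have a prior footing, because protocol section 2 names eGFR and BMI and section 3.2 makes maternal characteristics associated with elevated aPTT a secondary objective. That stands as clinical plausibility. It does not fix creatinine and obesity, or their coding, as adjusters of the arm effect.

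A reader might infer that the screen shaped the final model. The SAP does not support this: it gives clinical relevance as the basis for both covariates.

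A reader might also infer that creatinine was measured after randomisation, because section 10.2 says, after an elevated aPTT, to "adjust heparin dose and repeat aPTT, anti-Xa, and serum creatinine per protocol". But section 10.1 has "Collect blood for clinical laboratory tests (CBC, aPTT, anti-Xa, serum creatinine" on Day 1, and the Appendix 2 schedule marks creatinine at Day 1 only, in both arms. Baseline is the natural reading and needs only confirmation.

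On the estimator, the models have already been fitted, so a design-stage probability says nothing about what happened, and it depends on an unsourced 3%. Moving to Firth now is itself a choice made after the data were seen. It is also more liberal than Fisher, which the SAP allows, and its coverage was checked only without covariates. All of this stands. It is why the small-sample estimate should sit beside a finite ordinary one, be disclosed as post hoc, and carry no significance claim.

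**Conclusion.** The point holds and is minor. The covariate set for the adjusted odds ratio was not pre-specified in any document available here, and the a priori wording blurs that. An earlier dated SAP fixing creatinine and obesity would settle this part in the sponsor's favour; none is among the public documents.

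The missing zero-cell provision is a real gap in the plan. Ordinary logistic regression would give no usable arm odds ratio in about half of trials at the plan's rates, and in 8.9–15.0% if the standard-arm rate were 10%. This assumes maximum likelihood, since the SAP names no other estimator.

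Two stronger readings go beyond the documents. One is that a zero cell occurred, or that the reported odds ratio is invalid: no observed counts are given. The other is that the primary result is compromised or the covariates were picked to favour one arm: the Chi-squared test was in the protocol, needs no covariates and is unaffected, and nothing links the choice of covariates to the size of the arm effect.

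**What to change.** 1. Label the creatinine- and obesity-adjusted odds ratio exploratory, with its covariate set not pre-specified. Keep the between-arm screen and the stepwise search as a record of what was done, but do not present them as a valid way to choose adjusters in a randomised trial.
2. State whether either arm had zero events. Report the unadjusted and adjusted arm odds ratios with a small-sample estimator: Firth with profile-likelihood intervals (the FIRTH option in SAS PROC LOGISTIC) or exact conditional. Show the ordinary maximum-likelihood result beside it when finite, and disclose that the estimator was chosen after the data were seen.
3. Take significance for the primary endpoint only from the Chi-squared/Fisher test, so that a significant Firth interval cannot override a non-significant Fisher result.
4. While editing, give the BMI cut-off for obesity and confirm that creatinine is the Day 1 value.

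**Cost.** Some SAP wording and a few lines of SAS on data already collected. The Firth estimate is shrunk: its median is 15.1 at 18 per arm or 16.3 at 23, against a true (0.4/0.6)/(0.03/0.97) = 21.6 at the plan's rates. Its upper limit is very wide when a cell is zero. Its coverage has not been checked for the adjusted model, and it does not cure 2.6 to 3.3 expected events per term.
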